### **1.3.3. Radiotherapy dose**

Radiotherapy will be administered at standard doses for radical treatment of the bladder with bladder-sparing intent. The radiotherapy schedule selected for this study has been widely used in several bladder preservation studies (James ND1, Hussain SA, Hall E, et al. Radiotherapy with or without chemotherapy in muscle-invasive bladder cancer. *N Engl J Med.* 2012 Apr 19;366(16):1477-88). 64 Gy in 32 fractions, given as 2 Gy/day (5 doses/week) at doses of 46 Gy to the minor pelvis (23 doses) and 64-66 Gy to the bladder (32 doses) will be administered.

## **1.4. Benefit-risk and ethical assessment**

### **1.4.1. Durvalumab + tremelimumab**

#### *1.4.1.1. Overall risks*

Monoclonal antibodies directed against immune checkpoint proteins, such as programmed cell death ligand 1 (PD-L1) as well as those directed against programmed cell death-1 (PD-1) or cytotoxic T-lymphocyte antigen-4 (CTLA-4), aim to boost endogenous immune responses directed against tumor cells. By stimulating the immune system however, there is the potential for adverse effects on other tissues.

Most adverse drug reactions seen with the immune checkpoint inhibitor class of agents are thought to be because of inflammatory cells on specific tissues. These risks are generally events with a potential inflammatory mechanism and which may require more frequent monitoring and/or unique interventions such as immunosuppressants and/or endocrine replacement therapy. These risks include gastrointestinal AEs such as colitis and diarrhoea, pneumonitis /interstitial lung disease (ILD), renal AEs such as, nephritis and increases in creatinine, hepatic AEs such as hepatitis and liver enzyme elevations, skin events such as rash and dermatitis, endocrinopathies such as hypo- and hyperthyroidism, hypophysitis, adrenal insufficiency, diabetes mellitus type I and diabetes insipidus, and neurotoxicities such as myasthenia gravis and Guillain-Barre syndrome.

#### *1.4.1.2. Durvalumab*

##### *ADRs in durvalumab monotherapy*

The identified risks with durvalumab monotherapy include the following: cough/productive cough, pneumonitis, ILD, dysphonia, ALT/AST increased, hepatitis, diarrhoea, abdominal pain, colitis, hypothyroidism, hyperthyroidism, blood TSH increased, blood TSH decreased, adrenal insufficiency, Type 1 diabetes mellitus, hypophysitis/hypopituitarism, diabetes insipidus, blood creatinine increased, dysuria, nephritis, rash, pruritus, night sweats, dermatitis, myocarditis, pyrexia, oedema peripheral, upper respiratory tract infections, pneumonia, oral candidiasis, dental and oral

soft tissue infections, influenza, myalgia, myositis, polymyositis and infusion-related reaction.

- *Potential imAEs for durvalumab and durvalumab in combination with tremelimumab include*
  - Pancreatitis
  - Other rare or less frequent events with a potential immune-mediated aetiology, eg, pericarditis, sarcoidosis, uveitis, and other events involving the eye (eg, keratitis and optic neuritis), skin (eg, scleroderma and vitiligo), and haematological (eg, haemolytic anaemia and immune thrombocytopenic purpura), rheumatological events (polymyalgia rheumatica and autoimmune arthritis) and neuropathy/neuromuscular toxicities (eg, myasthenia gravis, Guillain Barre syndrome)
- *Hypersensitivity reactions including:*
  - Anaphylaxis and allergic reaction
  - Cytokine release syndrome
  - Immune complex disease
- Other infections

A detailed summary of durvalumab monotherapy AE data can be found in the current version of the durvalumab IB.

In monotherapy clinical studies AEs (all grades) reported very commonly ( $\geq 10\%$  of patients) are fatigue, nausea, decreased appetite, dyspnea, cough, constipation, diarrhea, vomiting, back pain, pyrexia, abdominal pain, anemia, arthralgia, peripheral edema, headache, rash, and pruritus. Approximately 8% of patients experienced an AE that resulted in permanent discontinuation of durvalumab. and approximately 5% of patients experienced an SAE that was related to durvalumab by the study investigator.

The majority of treatment-related AEs were manageable with dose delays, symptomatic treatment, and in the case of events suspected to have an immune basis, the use of established treatment guidelines for immune-mediated toxicity (see the Dosing Modification and Toxicity Management Guidelines in appendix 1).

A detailed summary of durvalumab monotherapy AE data can be found in the current version of the durvalumab IB.

#### *1.4.1.3. Tremelimumab*

Risks with tremelimumab monotherapy are GI effects (colitis, diarrhoea, enterocolitis and intestinal perforation), endocrine disorders (hypo and hyperthyroidism, hypophysitis and adrenal insufficiency), skin effects (rash, and pruritus), elevations in lipase and amylase,

other gastrointestinal events e.g. ulcerative colitis, dehydration, nausea and vomiting; hepatic events including hepatitis, and liver enzyme elevations; pneumonitis and ILD; clinical manifestations of pancreatitis; nervous system events including encephalitis, peripheral motor and sensory neuropathies, Guillain-Barre and proximal muscle weakness; cytopenias including thrombocytopenia, anemia and neutropenia; infusion-related reactions, anaphylaxis, and allergic reactions; renal events including renal failure, acute kidney injury, nephritis, nephrotic syndrome, autoimmune nephritis and electrolyte abnormalities such as hypokalemia; autoimmune diseases including autoimmune arthritis, Sjögren's syndrome and giant cell temporal arteritis; hyperglycemia and diabetes mellitus; and pyrexia (Comin-Anduix B, Escuin-Ordinas H., 2016).

Further information on these risks can be found in the current version of the tremelimumab IB.

Using pooled data from monotherapy clinical studies AEs (all grades) reported very commonly ( $\geq 10\%$  of patients) were diarrhea, nausea, fatigue, pruritus, decreased appetite, rash, vomiting, dyspnea, constipation, cough, pyrexia, abdominal pain, decreased weight, headache, asthenia, and anaemia. Approximately 16% of patients experienced an AE that resulted in permanent discontinuation of tremelimumab and approximately 45% of patients experienced an SAE.

A detailed summary of tremelimumab monotherapy AE data can be found in the current version of the tremelimumab IB.

#### **1.4.2. Durvalumab + tremelimumab**

The safety of durvalumab + tremelimumab combination therapy is being evaluated in the ongoing dose escalation and dose expansion Study 006, in patients with NSCLC, and has so far shown a manageable safety and tolerability profile.

The potential risks with the combination of durvalumab + tremelimumab are similar to those for durvalumab and tremelimumab monotherapy. Emerging data from study 006 and from combinations of other agents in the same class indicate an increased frequency and/or severity of some of these potential immune-mediated toxicities.

In durvalumab+tremelimumab combination studies at the dose of durvalumab 20 mg/kg and tremelimumab 1 mg/kg AEs (all grades) reported very commonly ( $\geq 10\%$  of patients) are fatigue, diarrhoea, nausea, dyspnea, decreased appetite, pruritus, vomiting, anaemia, constipation, cough, abdominal pain, pyrexia, back pain, hyponatremia and rash.

Approximately 13% of patients experienced an AE that resulted in permanent discontinuation of study drug and approximately 13% of patients experienced an SAE

that was related to durvalumab and tremelimumab by the study investigator (Scott Antonia, Sarah B 2016).

A detailed summary of durvalumab + tremelimumab combination AE data can be found in the current version of the durvalumab IB.

## **2. STUDY OBJECTIVE**

### **2.1. Primary objective(s)**

To determine the efficacy of durvalumab plus tremelimumab with concurrent radiotherapy in terms of pathological response rate in patients with localized muscle invasive bladder cancer treated with bladder preservation intent.

### **2.2. Secondary objective(s)**

- To determine the rate of patients with bladder preserved, the rate of immediate and late salvage cystectomies and the survival with bladder preserved free of tumor, defined as the time from the start of immunotherapy to either the date of cystectomy or the date of recurrence of muscle- invasive bladder carcinoma or metastasis.
- To determine the disease-free survival, defined as the time from the start of therapy to the date of recurrence of muscle invasive bladder carcinoma or metastases, and overall survival, defined as the time from the start of immunotherapy to the date of death due to any cause
- To assess the safety profile and tolerability of the combination of durvalumab plus tremelimumab with concurrent radiotherapy
- To evaluate the long-term functionalism and late sequelae of the treatment in the preserved bladders

### **2.3. Exploratory objective(s)**

An associated translational study will be performed to analyze and characterize changes in the tumor cell and inflammatory stroma induced by the study treatment, in patients with poor response. Additionally, the predictive value of immune biomarkers on response and bladder preservation will be explored.

## **3. STUDY DESIGN**

### **3.1. Overview of study design**

This is an open-label, multicenter, phase II trial of the combination of durvalumab plus tremelimumab with concurrent normofractionated radiotherapy in patients with localized muscle invasive bladder cancer treated with a selective multimodality bladder conservative approach. The study will be conducted in a small group of centers with multidisciplinary teams with wide experience in multimodality bladder preservation therapy (7 centers belonging to SOGUG).

The treatment consisted of initial transurethral resection (TUR) of the tumor, with multiple random biopsies of normal-appearing bladder urothelium, followed by durvalumab 1500 mg i.v. plus tremelimumab 75 mg i.v., every 4 weeks for a total of 3

doses. Two weeks after the initiation of immunotherapy, normofractionated external-beam radiotherapy with high-energy photons will be started. Radiotherapy will be administered concurrently with immunotherapy at doses of 46 Gy to the minor pelvis and 64-66 Gy to the bladder. Six weeks after the end of radiotherapy as an efficacy determination, ALL patients will undergo a new cystoscopy with biopsies of the tumor bed and all residual present lesions. Response is defined as an absence of invasive cancer at post immunotherapy biopsy ( $\leq$ cT1). Patients with response to immunotherapy will be candidates to bladder preservation, whereas in those with residual muscle invasive tumor the possibility of salvage radical cystectomy must be evaluated. Patients developing an isolated bladder invasive relapse during follow-up will be also possible candidates to salvage cystectomy, whereas those developing a superficial relapse in the preserved bladder will be managed with TUR and intravesical BCG.

To monitor accurately the potential toxicity of radiotherapy associated with durvalumab and tremelimumab, an initial cohort of 5 patients of first Simon Optimax stage of 12 patients, will be treated. If no dose limiting toxicity is observed in  $\geq$ 2 of these patients in the 12 weeks of observation period, the rest of patients will be treated at full doses. In contrast, if severe toxicity is observed in  $\geq$ 2 of these patients, 3 additional patients will be treated. If dose limiting toxicity is seen in one of these additional patients, the therapeutic regimen will be modified in the subsequent ones, administering full doses of durvalumab but discontinuing tremelimumab after the first dose.

Patients will be followed up every 3 months the first year, every 4 months the second year and every 6 months thereafter with abdomen and pelvis CT scan, Rx thorax, urine cytology. Additional cystoscopy and bladder biopsy will be performed anytime in case of detection abnormalities in the cytology or imaging studies. The study will be closed 2 years after the last patient inclusion.

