***Study Assessments and Criteria for Evaluation:***

***Safety Assessments:***

Toxicity of the treatment will be assessed and graded using Common Terminology Criteria for Adverse Events CTCAE v4.03 and the Toxicity criteria of the Radiation Therapy Oncology Group (RTOG) and the European Organization for Research and Treatment of Cancer (EORTC) criteria. Patients will be evaluated weekly from the start until the end of treatment (week 12).

To monitor accurately the potential toxicity of radiotherapy associated with durvalumab and tremelimumab, an initial cohort of 5 patients will be treated. If no dose limiting toxicity is observed in ≥2 of these patients (in observation period of 12 weeks (4 weeks after RT) , the rest of patients will be treated at full doses. In contrast, if severe toxicity is observed in ≥2 of these patients, 3 additional patients will be treated. If dose-limiting toxicity is seen in one of these additional patients during observation period, the therapeutic regimen will be modified in the subsequent ones, administering full doses of durvalumab but discontinuing tremelimumab after the first dose.

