### **6.1. Dose modification and toxicity management**

#### **6.1.1. Radiotherapy**

Patients who, for reasons unrelated to toxicity, discontinue radiotherapy for more than 2 weeks will be excluded from the study. In the case of interruptions of less than 2 weeks, the patient will resume treatment from the point where he was interrupted.

**A severe toxicity (G3-4) related to radiotherapy or due to combination of the RT+durvalumab/tremelimumab, RT will be suspended until recovery to G1. However, if it is toxicity unrelated to the RT, it will continue without variations.**

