#### **6.1.2. Durvalumab and tremelimumab**

Guidelines for the management of immune-mediated reactions, infusion-related reactions, and non-immune-mediated reactions for durvalumab monotherapy and durvalumab + tremelimumab are provided in the Dosing Modification and Toxicity Management Guidelines in Appendix 1. Patients should be thoroughly evaluated and appropriate efforts should be made to rule out neoplastic, infectious, metabolic, toxin, or other etiologic causes of the imAE. Serologic, immunologic, and histologic (biopsy) data, as appropriate, should be used to support an imAE diagnosis. In the absence of a clear alternative etiology, events should be considered potentially immune related.

In addition, there are certain circumstances in which durvalumab and tremelimumab should be permanently discontinued (see Section 4.4 of this protocol and the Dosing Modification and Toxicity Management Guidelines in Appendix 1).

Following the first dose of IP, subsequent administration of durvalumab and tremelimumab can be modified based on toxicities observed as described in the Dosing Modification and Toxicity Management Guidelines in Appendix 1. These guidelines have been prepared by the Sponsor to assist the Investigator in the exercise of his/her clinical judgment in treating these types of toxicities. These guidelines apply to AEs considered causally related to durvalumab monotherapy and the durvalumab + tremelimumab regimen by the reporting investigator.

**Dose reductions are not permitted.** In case of doubt, the Investigator should consult with the Study Physician. In case of severe grade 3-4 toxicity, the possibility to discontinue tremelimumab, following the administration of durvalumab alone concurrently with radiotherapy, when the toxicity will recover, should be considered.

It is planned to replace those patients who interrupt the trial in advance (without having completed 12 weeks of treatment) and have not presented dose-limiting toxicity. Patients who have not been taking durvalumab and tremelimumab for more than 21 days or who discontinue treatment with radiotherapy for more than 2 weeks will also be replaced.

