### 11.2.3. Interim analyses

- **Safety:** To monitor accurately the potential toxicity of radiotherapy associated with durvalumab and tremelimumab, an initial cohort of 5 patients will be treated. If no dose limiting toxicity is observed in  $\geq 2$  of these patients at the end of the treatment, the rest of patients will be treated at full doses. In contrast, if severe toxicity is observed in  $\geq 2$  of these patients, 3 additional patients will be treated. If dose limiting toxicity is seen in one of these additional patients, the therapeutic regimen will be modified in the subsequent ones, administering full doses of durvalumab but discontinuing tremelimumab after the first dose.
- **Efficacy:** The study will be conducted using a Simon “Optimal design” two-stage sequential design. An interim analysis of response will be performed at the end of the first stage, after the treatment of the first twelve patients treated. Six or more responses in the first stage were required for continuation to second stage accrual.

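### The run-in rule sets no upper limit on toxicity among the first 5 patients, so 3, 4 or 5 of 5 is handled like 2 of 5

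*Combined protocol and SAP*

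**What the plan says.** The rule appears in three places: the synopsis (Safety Assessments), protocol section 3.1 and protocol section 11.2.3.

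- **Step one.** Five patients, part of the 12 in the first Simon stage, are treated and observed. Section 3.1 continues: "In contrast, if severe toxicity is observed in" 2 or more of them, then "3 additional patients will be treated". No upper end is given for that count.
- **Step two.** "If dose limiting toxicity is seen in one of these additional patients, the therapeutic regimen will be modified in the subsequent ones". The synopsis words the trigger as "If dose-limiting toxicity is seen in one of these additional patients during observation period", and section 11.2.3 as "If dose limiting toxicity is seen in one of these additional patients, the therapeutic regimen will be modified". All three refer to the added patients only.
- **The modification.** It consists of "administering full doses of durvalumab but discontinuing tremelimumab after the first dose". No change to radiotherapy is stated.

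The text does not say what follows 0 of 3, which dose the added 3 receive, or what counts as dose-limiting. Step one triggers expansion on severe toxicity, and step two triggers modification on dose-limiting toxicity.

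Other safety provisions act on individual patients or leave the decision open:

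- Section 6.1.1, for related grade 3-4 events: "RT will be suspended until recovery to G1".
- Section 6.1.2: "In case of severe grade 3-4 toxicity, the possibility to discontinue tremelimumab" is to be considered.
- Appendix 1 stops study drug for grade 4 immune-mediated events, with some exceptions.
- Section 4.4 lets the sponsor request that a patient's dosing stop.
- Section 11.2.1 schedules weekly safety analysis.
- Sections 14.3 and 14.4 give the sponsor discretion to end the study or amend the protocol.

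**The concern.** The run-in is the plan's only cohort-level toxicity count, and it exists to test this combination before wider exposure. An outcome in which most of the first cohort has severe toxicity is the one where the count matters most. There the rule makes no distinction: 5 of 5 leads to the same action as 2 of 5. The regimen changes only for patients after the added 3, so those 3 would start it unmodified whatever happened to the first 5.

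At stake is the exposure of 3 patients to tremelimumab doses that the protocol itself would withdraw, and a written rule that is silent on its own worst results.

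**Working it through.** The plan states no operating characteristics for the run-in, so there is no figure to reproduce.

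**Inputs from the documents.** First cohort 5; expansion at 2 or more; expansion size 3; modification if a dose-limiting event is seen in one of the 3, read as at least one.

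**Assumptions.**
1. The documents give no toxicity rate for immunotherapy plus radiotherapy, so the true rate p is varied from 10% to 50%.
2. 0 or 1 of 5 means full doses continue. The sentence for that branch is awkwardly worded, but the contrast with 2 or more implies this split.
3. The added 3 receive unmodified treatment, because modification applies only to later patients.
4. For columns D to F only: 0 of 3 means no change, and severe and dose-limiting are the same event. The text states neither.
5. The sponsor takes no action outside the rule.

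**Formulas.** X ~ Bin(5, p) is the count in the first cohort.
- B = P(X≥3). At p = 0.3: 10(0.3)³(0.7)² + 5(0.3)⁴(0.7) + (0.3)⁵ = 0.1323 + 0.0284 + 0.0024 = 0.163.
- C = expected avoidable tremelimumab doses = B × 3 patients × 2 doses. The modified regimen keeps the first tremelimumab dose and full durvalumab, so only doses 2 and 3 are avoidable. This is an upper bound, because individual stopping rules reduce it.
- D = P(X≥3)(1−p)³, that is, 3 or more of 5 followed by 0 of 3.
- E = P(X=3)(1−p)³, the part of D that ties with 2+1 at 3 of 8.
- F = P(X≥4)(1−p)³, the part of D with a strictly higher total than 2+1.

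| p | B | C | D | E | F |
|---|---|---|---|---|---|
| 10% | 0.9% | 0.05 | 0.6% | 0.6% | 0.03% |
| 20% | 5.8% | 0.35 | 3.0% | 2.6% | 0.3% |
| 30% | 16.3% | 0.98 | 5.6% | 4.5% | 1.1% |
| 40% | 31.7% | 1.90 | 6.9% | 5.0% | 1.9% |
| 50% | 50.0% | 3.00 | 6.2% | 3.9% | 2.3% |

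Columns B and C do not use assumption 4.

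**Effect of a cap at 3 of 5.** Let q be the step-two event rate. As written, a patient group with X≥3 goes unmodified with probability (1−q)³; with the cap it is always modified. The other branches are unchanged, so the chance of modification rises by P(X≥3)(1−q)³ and cannot fall.
- If q = p, the rise is column D: 0.6, 3.0, 5.6, 6.9 and 6.2 points.
- If q = p/2 (dose-limiting events half as frequent as severe ones), it is 0.7, 4.2, 10.0, 16.3 and 21.1 points. At p = 0.2: 0.0579 × 0.9³ = 0.042.

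**The case against.** A reader might infer something stronger: that the rule is inverted, because 2+1 (3 of 8) changes the regimen while 3+0, 4+0 and 5+0 (3, 4 and 5 of 8) do not. The documents do not support this as a finding. It needs two unwritten readings: that 0 of 3 means no change, and that severe and dose-limiting are the same event. Sections 6.1.1 and 6.1.2 attach grade 3-4 to the word severe, while dose-limiting is left undefined. A sensitive first screen followed by a stricter confirmatory trigger would be a coherent design, and the totals would then not be like for like. Even granting both readings, strictly higher totals are rare (column F).

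Low rates also deserve weight. Section 1.3.1 reports no dose-limiting toxicity in the cohort given 20 mg/kg durvalumab with 1 mg/kg tremelimumab, and section 1.4.2 gives about 13% related serious events for the two drugs. Radiotherapy may raise these, so they are not the rate here. At 13%, though, 3 or more of 5 has probability only 1.8%.

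The sponsor would probably intervene after 4 of 5, and sections 4.4, 14.3 and 14.4 allow it. That limits the practical harm but supplies no number, and the written rule still directs 3 more patients into treatment.

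Finally, the run-in is probably complete: section 3.1 of the analysis document describes 32 patients, all with at least 2 durvalumab doses and 3 weeks of radiotherapy. This lowers the priority of new wording. It does not make the rule sound.

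**Conclusion.** The point holds in a limited form. All three statements of the rule leave the first 5 patients without an upper limit, so 3, 4 or 5 of 5 with severe toxicity leads to the same step as 2 of 5, and 3 more patients start a regimen that the text does not modify. This rests on the wording that confines modification to later patients. It does not depend on what 0 of 3 means or on whether the two toxicity terms coincide.

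The chance of reaching this branch is negligible at a 10% rate and substantial at 40% or more. The consequence is bounded at 6 tremelimumab doses in total, 2 in each of 3 patients. Less caution after a higher total is only a conditional possibility, at most about 2.3% over the assumed range. Minor priority.

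**What to change.** In the synopsis, section 3.1 and section 11.2.3, leave the branches for 0-1 and 2 of 5 and the step-two trigger as they are, and add two statements:

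- If 3 or more of the first 5 have severe toxicity (the step-one event), later patients receive the modified regimen at once, without 3 more on unmodified treatment.
- If 2 of 5 is followed by 0 of 3, treatment continues at full doses.

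Do not merge the two triggers into a single unnamed event counted over all 8. Suppose dose-limiting events are half as frequent as severe ones. The present rule then modifies with probability 7.1%, 18.2%, 32.4% and 47.0% at severe rates of 20% to 50%. A cumulative limit of 3 dose-limiting events would lower that to 2.8%, 8.0%, 15.8% and 25.6%.

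If the run-in is already complete, report how many of the first 5 (and of any added 3) had severe and dose-limiting toxicity, and what was decided. The safety tables in the analysis document (Tables 198-208) have no row for this, so one small table is needed.

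The cost is a few lines of wording and that table, with no extra patients. The downside is more frequent modification when the regimen is tolerable: 0.6 points at a 10% rate and 3.0 points at 20% if the two terms coincide, or 0.7 and 4.2 points if dose-limiting events are half as frequent. The documents state no acceptable toxicity rate, so the limit of 3 of 5 remains a judgement for the sponsor to confirm.
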